4.1.5. Independent Data Monitoring Committee

Given the well-established safety and efficacy data for CAB and RPV LA from multiple prior studies including LATTE-2, ATLAS, FLAIR, and ATLAS-2M, coupled with a well characterized safety profile of the comparator arm (BIK), the SOLAR study team in consultation with the ViiV Safety and Labeling Committee (VSLC) decided that no formal IDMC or iSRC is warranted for this study.

Furthermore, accumulating study data from this study will be regularly reviewed in aggregate by the CAB Safety Review Team (SRT). Any new, emerging safety signals detected by the SRT will be acted upon by the study team. An interim analysis is planned to review primary and secondary efficacy data and key safety data when all participant complete Month 6 visit. These actions will provide comprehensive data monitoring for the study in the absence of IDMC.

4.2. Type and Number of Participants

The target population to be enrolled is HIV-1 infected, virologically suppressed (HIV-1 RNA <50 c/mL) participants on a BIK single tablet regimen.

It is anticipated that approximately 654 participants will be enrolled into SOLAR. A 15% screen failure rate is anticipated. Participants will be enrolled from multiple countries including (but not limited to) Canada, UK, Ireland, France, Germany, Spain, Italy, Switzerland, Austria, Netherlands, Belgium, Japan, Australia, and the United States.

Randomization will be stratified by gender at birth and BMI. A goal of this study is to enroll populations who are underrepresented in clinical studies, including approximately

20% women. Sites are expected to take into account gender in their screening strategies in order to achieve women enrolment. .

4.3. Scientific Rationale for Study Design

The design of this study (2:1 randomized, open-label, active-controlled, multicenter, parallel group, non-inferiority study) is well established for confirming the non-inferiority of an investigational agent compared with an active comparator and is generally accepted by regulatory authorities as rigorous proof of antiviral activity. The primary endpoint, proportion of participants defined as virologic failures by the FDA Snapshot algorithm is recommended in the FDA's 2015 guidance document [CDER, 2015] for assessing efficacy in Switch Trials. The key secondary endpoints, proportion with plasma HIV-1 RNA <50 c/mL at Month 6 and Month 12, is also a well-established surrogate endpoint for prognosis of HIV-1 infection and disease progression. The Extension Phase will allow for a collection of longer-term efficacy, safety and tolerability data for the CAB LA + RPV LA Q2M regimen.

Various approaches to simplify a patient's antiretroviral therapy (ART) regimen, after achieving viral suppression, have been studied. Previous studies have evaluated switches to ritonavir-boosted PI monotherapy therapy in virologically suppressed patients [Bierman, 2009 and Arribas, 2012]. While the data from these studies have shown both long-term non-inferiority and inferiority to continual Highly Active Antiretroviral Therapy (HAART), they suggest that simplifying from a three-drug dual class regimen to a single boosted protease inhibitor may be a safe and effective option for the majority of participants studied who have effectively maintained viral suppression.

The 200056 (LATTE-2) [GlaxoSmithKline Document Number 2013N168152_09, 2017] and the ATLAS-2M [GlaxoSmithKline Document Number 2017N326521_02, 2018] clinical trials evaluated a different simplification approach and served as proof of concept for this study. In 200056, HIV-1 RNA suppression was induced with a three-drug antiretroviral regimen consisting of CAB + ABC/3TC FDC, and then participants switched to a two-drug two-class regimen consisting of CAB LA + RPV LA for the maintenance of HIV-1 RNA suppression. Results demonstrate that through 96 weeks on two-drug maintenance therapy, 94% (Q8W IM arm) and 87% (Q4W IM) of participants maintained virologic suppression (HIV-1 RNA <50 c/mL) compared to 84% of participants continuing oral CAB + 2 NRTIs. CAB LA + RPV LA was well tolerated through Week 96 for both the Q8W and Q4W dosing regimens, as demonstrated by a low discontinuation rate due to AEs, including injection site reaction (ISR) related AEs in either dosing arm, with no significant dose-dependent trends in safety parameters. On the basis of 200056 Week 48, and Week 96 data, Q4W and Q8W IM dosing are being progressed into Phase 3 for further clinical development, respectively. In 207966, 1.7% of participants in the CAB + RPV Q8W group and 1.0% of participants in the CAB + RPV Q4W group met the primary efficacy endpoint of plasma HIV-1 RNA ≥ 50 c/mL at Week 48. Based on a 4% non-inferiority margin, CAB + RPV Q8W is non-inferior to CAB + RPV Q4W at Week 48 because the upper bound of the 95% CI for the adjusted treatment difference [0.8 (-0.6, 2.2)] is less than 4%.

The open-label design for 213500 (SOLAR) best suits the objectives of this study. A double-blind, double-dummy design for this study would result in an increased pill burden in all participants, a requirement for placebo injections across the comparator arms, elevated risk of oral ART non-adherence in participants receiving placebo injections, limitations to patient reported preference data comparing injectable and oral ART, as well as considerable trial design complexities. A blinded design is also complicated by the requirement for an oral lead-in, in participants who elect to receive this short-term regimen at the start of study before the initiation of CAB LA + RPV LA injections. Blinding the oral lead-in would require additional placebo pills for 5 weeks in the ART continuation arm, that otherwise would not be required. This study utilizes a 2:1 randomization that provides advantages with respect to costs, gathering additional safety information, reduces the effect of any learning curves due to injection administration or metabolic testing and improves recruitment.

In addition to study design challenges, the impact of blinding carries the potential risk of oral regimen non-compliance, in participants on the ART continuation arm, who may believe that they are receiving active drug via injection (and therefore possibly increased risk of HIV transmission to uninfected partners). The additional risk of inadvertent non-adherence to oral ART outweighs any benefits that may be gained through a blinded design.

Importantly, a key objective for the planned Phase 3 studies is to understand the acceptability and patient reported preferences to this novel injectable regimen, relative to daily oral standard of care (SOC) ART. An unblinded study design supports collection of participant preference data in a way that would not be possible if a double-blind, double-dummy design were implemented. Due to the complexities, limitations and risks of blinding, this study is planned as an open label study.

To maintain the integrity of the trial, data aggregated by actual treatment group will not be made available to members of the Study Team and will not be shared with Investigators until the primary analysis at Month 12. In addition, central stratified randomization will be used to ensure that selection bias is avoided (see Section 6.2). The stratification factors gender and BMI will be considered based on historical studies. Lastly, ascertainment bias affecting the primary efficacy analysis is unlikely since the primary endpoint is inherently objective, being primarily determined by HIV-1 RNA laboratory assessment. The open label design should therefore have no impact on the analysis of study endpoints.

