6.3.2. Blinding

This will be an open-label study and therefore no blinding is required. No summaries of the study data according to actual randomized treatment groups will be available to sponsor staff prior to the planned Month 6 interim analysis. Public presentation of the

Month 6 analysis will not be done prior to the last participant's Month 12 (OLI and BIK)/Month 11 (D2I) visit.

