9.4. Statistical Analyses

The statistical analysis plan will be finalized prior to database freeze and it will include a more technical and detailed description of the statistical analyses described in this section. This section is a summary of the planned statistical analyses of the most important endpoints including primary and key secondary endpoints.

The study design is open label. However, the central ViiV/GSK team responsible for the conduct and analysis of the study will not review any summaries of data grouped by treatment prior to database freeze for the Month 6 interim analysis.

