9.5. Interim Analyses

The main analysis will be conducted to evaluate the primary objective of the protocol when all participants have completed their Month 12 (OLI and BIK)/Month 11 (D2I) visit. An interim analysis will be conducted when all participants have completed their Month 6 (OLI and BIK)/Month 5 (D2I) visit. To minimise bias, the Month 6 interim results will not be shared with any participant and with most investigators. However, when a lead author(s) for a potential abstract presentation of the Month 6 interim results

is (are) identified, that investigator(s) and the other co-authors on the abstract will have access to the interim results prior to its presentation. No other investigators will have knowledge of this data prior to the last participant completing their last visit for the primary Month 12 analysis. A Month 6 interim analysis abstract may be submitted to a conference for consideration only if the conference convenes after the Month 12 data collection has been completed.

The interim analyses will include analyses on the primary and secondary efficacy endpoints, as well as key safety endpoints. Full details of the interim analyses will be specified in the Reporting and Analysis Plan (RAP).

Further data cuts and analyses may be conducted as necessary to support regulatory submissions, publications or for other purposes. Additionally, information collected on pregnant participants as collected in the eCRF may be reported descriptively or listed on an interim basis (see [Appendix 6](#) for further details). No adjustment for multiplicity caused by repeated analysis on the primary endpoint will be made as the interim analysis will be secondary. Type I error rate will not be inflated for the treatment comparison at the final analysis as non-inferiority will not be assessed at the interim.

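### Section 4.3 says by-arm data stay closed to the Study Team and Investigators until Month 12, but Sections 6.3.2, 9.4 and 9.5 open them from Month 6; the rules cannot all be followed.

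*Protocol*

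**What the plan says.** Section 4.3 gives three reasons why an open-label design is acceptable. The first is an access rule: "data aggregated by actual treatment group will not be made available to members of the Study Team and will not be shared with Investigators". It sets the end of that bar at the Month 12 primary analysis. The other two reasons are central stratified randomization and a primary endpoint that rests mainly on a laboratory HIV-1 RNA result. It then concludes: "The open label design should therefore have no impact on the analysis of study endpoints".

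Later sections set other limits:

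- **Section 6.3.2:** no summaries by randomized group "will be available to sponsor staff prior to the planned Month 6 interim analysis". Public presentation of the Month 6 results is held until the last participant's Month 12 (or Month 11) visit.
- **Section 9.4:** the central team that conducts and analyses the study "will not review any summaries of data grouped by treatment prior to database freeze for the Month 6 interim analysis".
- **Section 9.5:** the interim covers the primary and secondary efficacy endpoints and key safety. Once a lead author for an abstract is identified, "that investigator(s) and the other co-authors on the abstract will have access to the interim results prior to its presentation". Other investigators stay barred until the last participant's final visit for the Month 12 analysis, and participants are not shown the results.
- **Section 4.1.5:** there is no IDMC. "An interim analysis is planned to review primary and secondary efficacy data and key safety data when all participant complete Month 6 visit", and this is offered as part of the monitoring that stands in for one.

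On the timing of the analysis plan, Section 9.4 says: "The statistical analysis plan will be finalized prior to database freeze". That sentence does not say which freeze.

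**The concern.** Section 4.3 claims a property that the rest of the protocol does not deliver. Of its three protections, only the access rule deals with knowledge of accumulating comparative results. Central randomization prevents foreknowledge of the next assignment, and a laboratory endpoint limits subjective assessment. Neither stops people who know how the arms are doing from acting on it.

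Decisions remain open after Month 6. Investigators may discontinue participants at their discretion (Section 7.1). The Medical Monitor rules on oral bridging (6.8.1), on dosing outside the window (6.9.1) and, with the investigator, on whether a participant needing a prohibited medication may stay (7.1). Section 9.4.1 leaves it optional whether viral loads after a confirmed pregnancy are censored in the Snapshot analysis, in a trial where only the long-acting arm may continue through pregnancy. If such choices are made by people who have seen by-arm efficacy, with no independent committee in between, the result is open to challenge even if nobody acts improperly.

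**Working it through.** **1. The access rules side by side (all current text)**

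| Section | Who is barred | Until when |
|---|---|---|
| 4.3 | Study Team and Investigators | Month 12 primary analysis |
| 6.3.2 | Sponsor staff | Month 6 interim |
| 9.4 | Central conduct-and-analysis team | Month 6 database freeze |
| 9.5 | Investigators other than abstract authors | Last participant's Month 12 analysis visit |

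For the sponsor team, 4.3 gives Month 12 while 6.3.2 and 9.4 give Month 6. Release at Month 6 is implied by where the bar ends; Section 9.5 itself names only authors. For investigators, 4.3 allows no exception and 9.5 makes one. No reading satisfies all four sections.

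**2. The plan's own figures**

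Inputs from Section 9.2.1 and Table 7: 436 and 218 participants, failure rates 2% and 1%, margin 4%, one-sided alpha 2.5%, Miettinen-Nurminen score test. Exact binomial enumeration of that test gives power of 85.1% against about 85% stated. The other rows of Table 7 give 81.1% (80% stated) and 90.8% (90% stated). Exact type I error at 5% versus 1% is 0.0238. None of these depends on who sees the interim, because Section 9.5 says non-inferiority is not assessed there.

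**3. How many events carry the conclusion**

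Expected failures: 436 × 0.02 = 8.7, about 9; 218 × 0.01 = 2.2, about 2. One event moves the difference by 1/436 = 0.23 points (long-acting) or 1/218 = 0.46 points (BIK).

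Unstratified Wald upper limit, d + 1.96 × √[p₁(1−p₁)/436 + p₂(1−p₂)/218]:

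- 9 v 2: 1.15% + 1.96 × 0.938% = 2.99%, below 4%.
- 12 v 2: 1.83% + 1.96 × 1.015% = 3.82%, below 4%.
- 13 v 2: 2.06% + 1.96 × 1.039% = 4.10%, above 4%.

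Four extra long-acting failures separate the two conclusions. This is illustrative; the planned analysis is stratified.

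**4. Share of primary visits still ahead when access opens**

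Assume uniform accrual over R months and a lag of L months from the last Month 6 visit to available results. The last participant reaches Month 6 at R + 6. Someone enrolled at time u has the primary visit at u + 12, which is still ahead if u > R − 6 + L. The share is min(1, (6 − L)/R). The six-month gap also holds for direct-to-injection participants (Month 5 to Month 11).

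| R (months) | L = 0 | L = 2 | L = 3 |
|---|---|---|---|
| 4 | 100% | 100% | 75% |
| 6 | 100% | 67% | 50% |
| 9 | 67% | 44% | 33% |
| 12 | 50% | 33% | 25% |

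Only R = 4 appears in the protocol, as an estimate for UK participants (Appendix 12). The other values of R and all values of L are assumptions. Access opens at the freeze, so L = 0 is an upper bound.

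**The case against.** The case for leaving the design alone has real substance.

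- **The release is limited.** Section 9.5 withholds the results from participants and from every non-author investigator, and allows an abstract only for a conference after Month 12 data collection. Section 6.3.2 bars earlier public presentation. The investigator exception is confined to authors. This stands.
- **Much is not discretionary.** Virologic failure is judged only on central-laboratory HIV-1 RNA. The retest for 50 to <200 c/mL at key visits and discontinuation of study treatment after confirmed failure are both mandatory. Sites already know each participant's arm, so what they gain is the aggregate result. This stands and narrows the risk.
- **The Month 6 rule looks deliberate.** The amendment history records that the 6.3.2 and 9.4 wording was added to match the analysis plan, so 4.3 may simply not have been updated. That is plausible, but then its conclusion was not updated either.
- **The freeze may be the Month 6 one.** It is the only freeze that Section 9.4 names, so it is a natural reading of the analysis-plan sentence. The timing point is therefore a request to say so, not a demonstrated error. The pregnancy rule is expressly left to the analysis plan, so its absence from the protocol is no fault; only its timing matters.

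A reader might infer more than the text supports. The trial does not lose its main safeguard: Section 4.3 ranks none of its three protections, and two remain. Type I error is not inflated. The undefined list of major protocol violators cannot decide the primary result, because the per-protocol set serves only a sensitivity analysis. A single reclassified event does not flip the expected result.

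**Conclusion.** The contradiction is real and rests on current text. As written, the protection in Section 4.3 does not exist between Month 6 and Month 12 for the sponsor team, or for any investigator who co-authors the interim abstract. The conclusion that the open-label design has no impact is therefore not supported as stated.

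The consequence is possible operational bias and weaker credibility; no bias has been quantified. Sample size, power and alpha stand. The exposure is bounded by two figures: about four long-acting failures between passing and failing at the planned rates, and 25% to 100% of primary visits still ahead under the assumed recruitment times and lags. That Section 9.5 releases results split by arm is an inference, though a firm one: it covers the primary endpoint, and 6.3.2 and 9.4 tie by-treatment summaries to the same analysis.

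**What to change.** State one access rule, in the same words, in Sections 4.3, 6.3.2, 9.4 and 9.5:

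- **(a) Investigators.** No site investigator, abstract authors included, sees by-arm Month 6 results until the last participant's Month 11/12 visit and any retest. The abstract is then prepared later or without site investigators. The loss is small, since Section 9.5 already rules out a conference before Month 12 data collection ends.
- **(b) Analysis plan.** Say in 9.4 that the plan for the primary analysis, including the rule for viral loads after pregnancy, is final before the Month 6 database freeze.
- **(c) Sponsor team.** Either keep by-arm Month 6 results from existing staff who make study-conduct decisions, or correct 4.3 to say that the sponsor team sees by-arm data from the Month 6 freeze, and withdraw or qualify the no-impact conclusion.

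The cost is amendment wording and earlier sign-off of the analysis plan. No participants are added. A newly created, separately staffed reporting group is not required.

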4.3.1. Participant Input into Design

Participants were not involved in the design of the clinical trial.

4.4. Justification for Dose

4.4.1. CAB + RPV

4.4.1.1. CAB and RPV Pharmacokinetics Following Q8W and Q4W Dosing

In pivotal Phase 3 studies 201585 and 201584 (ATLAS and FLAIR, CAB LA 400 mg + RPV LA 600 mg Q4W demonstrated non-inferiority to oral standard of care. In the Phase 3b Study 207966 (ATLAS 2M), CAB LA 600 mg + RPV LA 900 mg Q8W was non-inferior to the Q4W regimen while achieving lower overall trough concentrations. Participants naïve to CAB+RPV received CAB LA 600 mg + RPV LA 900 mg initiation injections at Week 4b (following a 4-week oral lead-in) and second (first continuation) injections at Week 8 regardless of regimen. Select trough concentrations following Q8W and Q4W dosing in ATLAS 2M are summarized in [Table 2](#).

Table 2 Summary of Evaluable Plasma CAB and RPV Trough Concentrations by Regimen at Select Visits for Participants with No Prior Exposure to CAB + RPV (Study 207966, ATLAS 2M)

Visit	Plasma CAB ($\mu\text{g/mL}$)				Plasma RPV (ng/mL)			
	n	Q8W (n=326)	n	Q4W (n=326)	n	Q8W (n=326)	n	Q4W (n=326)
Week 4 ^b	282	5.18 [4.93, 5.45] (45)	292	5.29 [5.04, 5.55] (43)	283	77.2 [72.8, 81.9] (54)	292	78.3 [73.6, 83.3] (58)
Week 8 ^c	273	1.57 [1.46, 1.69] (67)	267	1.52 [1.40, 1.64] (74)	272	48.2 [45.3, 51.2] (54)	267	45.5 [42.7, 48.4] (56)
Week 16	262	1.41 [1.32, 1.51] (58)	253	2.13 [2.02, 2.25] (46)	260	46.2 [44.0, 48.5] (41)	252	57.8 [54.6, 61.2] (49)
Week 24	219	1.44 [1.34, 1.56] (62)	228	2.41 [2.29, 2.54] (41)	220	49.5 [46.8, 52.3] (44)	228	63.4 [60.1, 67.0] (44)
Week 48	217	1.58 [1.49, 1.68] (47)	236	2.71 [2.58, 2.84] (39)	217	65.4 [61.9, 69.1] (43)	235	89.3 [84.5, 94.2] (44)

Data Source: 207966 CSR Table 4.5. GlaxoSmithKline Document Number [2019N406358_00](#), 2019]

a. Geometric mean [95% CI] (CVb%).

b. Represents trough at the end of 1-month oral lead-in prior to initiation injections.

c. Represents trough 4-weeks following CAB 600 mg and RPV 900 mg initiation injections prior to first continuation injections.

4.4.1.2. Q8W versus Every 2 Month Dosing

Separate population PK models for CAB LA and RPV LA that included concentration data from Phase 3 studies were developed and validated [GlaxoSmithKline Document Number [2019N421460_00](#), 2019 and GlaxoSmithKline Document Number [EDMS-ERI-198151177](#), 2019]. Simulations (including oral lead in) were performed to compare the impact of changing from Q8W (7 doses/year 1) to every other month dosing (6.5 doses/year 1). Differences between predicted trough concentrations following Q8W and every 2-month dosing are considered minimal ([Figure 1](#), [Figure 2](#)).

Figure 1 Comparison of CAB LA Q8W and Every 2 Months

[figure not shown]
[figure not shown]

Figure 2 Comparison of RPV LA Q8W and Every 2 Months

C_{min} , trough concentration; IM, intramuscular; LA, long acting; Q8W, every 8 weeks, RPV, rilpivirine.

[figure not shown]
For 1-week delays in dosing median CAB and RPV troughs decrease ~10% with 99% of participants predicted to have troughs above respective PA-IC90 values.

4.4.1.3. Optional Oral lead-in

The purpose of the oral lead-in is to assess the individual participant tolerability of CAB and RPV prior to administration of the prolonged release suspension injections. The impact of the oral lead-in on the CAB LA and RPV LA PK profiles is limited and it is not required for the achievement of either therapeutic or steady-state dose levels. In addition, participants are virologically suppressed upon initiation of CAB LA + RPV LA injections and will receive continuing contribution of the prior oral regimen to the overall antiviral activity if stopped the same day as initiation injections. Plasma concentrations at the end of the first dosing interval (4 weeks after injection) are similar with or without the prior oral lead-in (Figure 3, Figure 4). CCI

[figure not shown]
Participants opting to receive oral lead-in dosing will receive CAB 30 mg + RPV 25 mg once daily with food during the first month of the study.

Figure 3 Simulated Median (90% PI) CAB Concentration-Time Profiles for CAB LA 600 mg Initiation Injection with and without OLI

Reference lines: 0.166 µg/mL=PA-IC90; 0.65µg/mL=5th percentile predicted W8 trough following initiation injections in FLAIR and ATLAS; 13.1µg/mL= median Cmax following CAB 60 mg PO QD observed in LATTE

Figure 4 Simulated Median (90% PI) RPV Concentration-Time Profiles for RPV LA 900 mg Initiation Injection with and without OLI

